#### 9.5 Data management

All procedures for data storage, processing and management will comply with the Centre for Trial Research's Standard Operating Procedures and the Data Protection legislation. No identifiable data will be stored or linked to the clinical data received. The study statistician will carry out all analysis. All electronic data will be stored on fire walled university servers. Access to files will be through password protected PCs and only accessible to named researchers responsible for the running of the study and the Chief Investigator. EuroKing® and NNRD both have established procedures for the

TPL/003/2 v1.0

Page **21** of **38** 

transfer and receipt of patient-level NHS data. Data will be transferred by these organisations in line with their current procedures to ensure data security and confidentiality.

The online focus groups with professionals and lay members will be hosted on a Cardiff University secure server (sewtudb.cf.ac.uk) and access password protected. A member of the research team will act as administrator for the online focus groups. Individuals expressing interest will be provided with an electronic participant information sheet (PIS) explaining what participation will entail and what measures will be taken to protect their identity. Participation in the discussion will be taken as consent. Focus group participants will be provided with a password, enabling them to view and contribute to only the focus group to which they are affiliated.

Consent forms and transcripts of interviews and focus groups, conducted at NHS sites, will be stored in a locked filing cabinet, with keys available only to researchers and the Chief Investigator. Voice recordings from focus groups and interviews conducted at study sites will be made onto password protected encrypted memory cards and only transported between study sites and Cardiff University with an individual member of the study team or, if needed, by courier. Voice files will continue to be password protected and only accessible to relevant members of the study team following transfer to Cardiff University. Recordings will be transcribed in line with CTR's SOPs either within the department or by an approved transcription service. Participants of the qualitative component will be assigned a participant ID which will be used to label the transcripts. Transcripts will be anonymised and stored on the secure university server with access rights given only to those study members who require access.

All other essential documents generated by the study will be kept in the Study Master File (SMF) and/or the electronic SMF.

Cardiff University demonstrates compliance with current information governance (IG) requirements, as set out in the Department of Health Policy, with an IG toolkit score valid from 1 April 2018 of 88%. The IG Toolkit score for NNRD was 66% in 2016-17. The IG Toolkit score for EuroKing® 2015/ 2016 Ref: ASS 159120 was 83%.

#### 9.6 Cohort Study Statistical considerations

#### 9.6.1 Sample size

The non-inferiority of birth in water compared to birth on land on rates of OASIS will be examined by parity. The Birthplace in England study found that overall 4.6% and 1.6% of nulliparous and parous women respectively, sustained OASIS. A sample size of 15,000 nulliparous and 15,000 parous 'low risk' women (7,500 each water and land) is required to obtain 90% power, and a 95% one-sided confidence interval around a treatment difference of zero. A non-inferiority margin of 1% or less,

Page **22** of **38** 

and 0.6% or less will be taken as clinically non-significant amongst nulliparous and parous 'low risk' women respectively. Since nulliparous women birthing in water are regarded as the least prevalent of the four groups, a data collection period providing data on 7,500 would ensure adequate numbers in the other three, more prevalent groups. These data will be combined to assess the effects averaged across both strata at an increased power, with a combined required sample size of 30,000 'low risk' women. We have assumed that 25% of the 6,600 waterbirths recorded in EuroKing® in 2015 were nulliparous women (1650/annum). Allowing for staggered site set-up, five years of combined retrospective and prospective data collection would be required (January 2015 – November 2020). The exact ratio of nulliparous and parous women who give birth in water will be determined once the retrospective data are examined, but with increasing numbers of waterbirths, with 18 of the 35 EuroKing® using sites, collectively undertaking 6,037 waterbirths in 2016, we are confident the study will have sufficient power to answer this important clinical question.

For the neonatal primary outcome, an estimate of 5% is used for the proportion of babies born to 'low risk' mothers experiencing 'adverse neonatal outcome or treatment'. A non-inferiority margin of 1.0% or less will be taken as clinically non-significant. A sample size of 16,200 babies (8,100 per group water / land) are required to have 90% power, and a 95% one sided confidence interval around a treatment difference of zero. The identification of women who leave and do not leave the pool prior to delivery of the placenta can only be captured by addition of new data items in the prospective cohort. As delivery of placenta in water, or postpartum haemorrhage of >1,000 ml following waterbirth are relatively uncommon events (17% and 1% respectively) the proposed sample size of 30,000 women who use a birth pool will be underpowered to detect a difference in these outcomes, but will be described.

#### 9.6.2 Missing, unused & spurious data

Detail provided in the Statistical Analysis Plan (SAP).

#### 9.6.3 Procedures for reporting deviation(s) from the original SAP

These will be submitted as substantial amendments where applicable and recorded in subsequent versions of the protocol and SAP

#### 9.6.4 Inclusion in analysis

Women, and their babies, will be included in the study if the woman used water immersion at a study site during the period of data collection. For the purposes of providing denominator data and

Page 23 of 38

to fully answer the research objectives, a minimal data set will also be obtained on women at study sites who do not use water immersion.

To capture data relating to women who use any form of water immersion during labour 'use of a pool ' during labour, will pragmatically be being any women for whom water immersion analgesia is recorded in the EuroKing E3 system.

To capture births commenced in, but completed, out of water, such as in the event of shoulder dystocia or previously unrecognised breech presentation 'waterbirth' will be defined in the study as 'A birth in which the fetus is partially or totally expelled under water'.

Data relating to women and babies recorded in EuroKing as being 'Born Before Arrival' (BBA), or recorded as intentionally born without midwifery attendance, will be excluded from primary analysis.

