### 3 Study summary

The POOL Study is a cohort study with a nested qualitative component. The primary study aim is to establish whether for 'low-risk' women who use a pool during labour, waterbirth, compared to leaving a pool prior to birth, is as safe for mothers and babies. The criteria for women being 'low-risk' will follow criteria set out in the NICE Intrapartum Care Guidelines (1). Pool use during labour includes all forms of water immersion including permanent and temporary birth pools and conventional baths.

Primary study objectives are to:

- Evaluate if waterbirth is associated with an increase in adverse neonatal outcomes or treatment, to include asphyxia, infection, respiratory difficulties, and mortality; or maternal morbidity, particularly complex perineal trauma (Obstetric Anal Sphincter Injuries (OASIS)) and haemorrhage.
- 2. Assess the primary safety outcomes amongst the subgroups of nulliparous and parous women who were low risk at labour onset.
- Describe rates and treatment of haemorrhage for low risk women who, following birth in water, deliver the placenta underwater. This will also be described for women who leave the water prior to delivery of the placenta.

The secondary study objectives will set pool use and waterbirth in the context of NHS care. The study will describe:

- 1. The overall proportion and characteristics of women who use a pool for labour or birth, compared to those who do not use a pool.
- 2. The characteristics of, and outcomes for, women with identified risk factors at labour onset, who use a pool during labour.
- 3. The characteristics of, and outcomes for, women who develop labour complications who use a pool during labour.
- 4. Explore factors associated with high and low rates of pool use in individual maternity units.

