### 4 Background

During labour and birth water immersion is facilitated by use of a conventional bath or more frequently a specialist birthpool. All birthpools offer sufficient depth of warm water for the woman to be immersed to above her breasts when sitting and sufficient space for ease of movement and change of position. Simple inflatable pools are available, but NHS maternity units frequently now have pools which are plumbed in, some of which are more complex with inbuilt lighting and heating. Women enter the warm water in established labour, leaving the pool either prior to birth due to clinical concerns or maternal choice, or remaining in the pool until after birth of the baby. Some mothers remain in the pool until after delivery of the placenta. For mothers the potential benefits of waterbirth are considered to be pain reduction, relaxation, reduced labour interventions and reduced perineal trauma whilst for babies, a gentle birth and transition to life. It is suggested that waterbirth may also improve longer term outcomes; mother infant bonding, increased breastfeeding and enhanced maternal postnatal mental health.

In 1992 the House of Commons Health Committee recommended that hospitals should provide women with the use of a birth pool for labour '*where this is practicable*. In the intervening years the popularity of the use of water immersion for labour and birth in the UK has increased and NICE guidance has recommended since 20071.4 that water immersion analgesia should be made available to all clinically appropriate women in labour. The Cochrane review of water immersion during labour provided evidence supportive of pool use but could not answer the question relating to the safety of waterbirth. The review included 12 trials (3243 women), eight related to just the first stage of labour: one to early versus late immersion in the first stage of labour; two to the first and second stages; and another to the second stage only. Results for the first stage of labour found a significant reduction in the epidural/spinal/paracervical analgesia/anaesthesia rate amongst women allocated to water immersion compared to no immersion (478/1254 versus 529/1245; risk ratio (RR) 0.90; 95% confidence interval (Cl) 0.82 to 0.99, six trials). There was also a reduction in duration of the first stage of labour (mean difference -32.4 minutes; 95% Cl -58.7 to -6.13). There was no evidence

TPL/003/2 v1.0

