Page **12** of **38** 

of a difference in the rates of assisted vaginal deliveries (RR 0.86; 95% CI 0.71 to 1.05, seven trials), caesarean sections (RR 1.21; 95% CI 0.87 to 1.68, eight trials), use of oxytocin for augmentation (RR 0.64; 95%CI 0.32 to 1.28, five trials), perineal trauma or maternal infection. Of the three trials that compared water immersion during the second stage with no immersion, one trial found a significantly lower level of maternal satisfaction with the birth experience out of water (RR 0.24; 95% CI 0.07 to 0.80). The outcomes for babies following waterbirth has more recently been reported in a systematic review of 29 studies. Whilst the review found no evidence of a difference in clinically important neonatal outcomes for babies born in water, it concluded that a large multicentred study to address the question of the safety of waterbirth for babies is now a priority.

The analgesic properties of water immersion during labour make the option attractive to women and the relatively low cost of the purchase and installation of birthpools, at around £5,000 per pool, makes this a reasonable facility to be provided within NHS premises. Whilst the provision of birthpools are desirable in order to provide women with comfort in labour, if waterbirth is associated with an increase in adverse maternal or neonatal outcomes the potential economic and social costs, could be very high. Several case reports have highlighted potential safety issues for babies that are manifest in the days after birth. Some potential adverse outcomes of clinical interest are specific to waterbirth such as neonatal water inhalation, whilst for other outcomes, being in a pool has the potential to adversely influence outcomes, such as in the time-critical emergency management of shoulder dystocia, which could potentially be delayed due to the need to move the woman from the pool. Such adverse outcomes, in addition being devastating to families are costly to the NHS with a daily tariff for neonatal intensive care at £1,081 and settlements for cerebral palsy resulting from clinical negligence with potential values of over £10m^8. Whilst water immersion is accepted to provide effective labour analgesia, evidence continues to be lacking as to whether women should be encouraged to leave, or remain in, the pool for birth.

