### 5.4 Secondary Outcomes

Secondary outcomes of parental, clinical and financial importance have been identified. Data relating to maternal or neonatal readmission to hospital within seven days of birth is already reported by community midwives and captured in EuroKing® systems at the point of discharge from midwifery care. Data relating to some primary and secondary outcomes are not currently captured in EuroKing® maternity information systems and at site opening the EuroKing® E3 systems at sites will be amended to prospectively collect these data.

Maternal secondary outcomes: Maternal Intrapartum: Shoulder dystocia and required management, management of the third stage of labour, need and reason for obstetric involvement in woman's care including sepsis; mode of birth, maternal position at birth, treatment for haemorrhage, incidence and management of perineal and other genital trauma. Maternal Postnatal: duration of postnatal stay, breast feeding initiation and continuation, higher level care, and maternal readmission to hospital within seven days of birth.

Infant secondary outcomes: Snapped umbilical cord prior to clamping, skin to skin contact at birth, timing of cord clamping, resuscitation, Apgar scores, administration and duration of intravenous antibiotics. Incidence of: lumbar puncture, culture proven infection, brachial plexus injury; treatment for jaundice; readmission to hospital within seven days of birth; therapeutic hypothermia;

TPL/003/2 v1.0

Page **15** of **38** 

neonatal unit admission and duration; cause of neonatal death; respiratory support. Where available, and where the risk status and pool usage of mothers can be determined, retrospective data will be used in addition to prospective data, to describe the occurrence of these infant outcomes.

Additional data items with accompanying background development required to fully answer the research aims will be added to E3 systems at study sites, and will include:

- Maternal risk factors at pool entry
- Maternal risk factors developing during labour
- Time of entry into pool
- Time of last leaving pool
- Reason for leaving pool if prior to birth
- Partial birth in water (breech / shoulder dystocia)
- Birth position in pool
- Conversion from planned physiological to active third stage labour management.
- Delivery of placenta in or out of water
- Treatment for haemorrhage
- Reason for obstetric involvement in woman's care

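### Pool use rests on a water immersion analgesia entry with no timing element: waterbirths without that entry are left unresolved, and early voluntary leavers enter the comparator with no stated analysis of leaving time

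*Protocol*

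**What the plan says.** Section 9.6.4 opens broadly: women and babies are "included in the study if the woman used water immersion at a study site during the period of data collection". It then gives a working rule. "To capture data relating to women who use any form of water immersion during labour", pool use is taken to be "any women for whom water immersion analgesia is recorded in the EuroKing E3 system". Section 3 states the scope: "Pool use during labour includes all forms of water immersion including permanent and temporary birth pools and conventional baths".

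Waterbirth is defined separately in 9.6.4 as "A birth in which the fetus is partially or totally expelled under water". Section 7 says that data on waterbirth are already captured in the maternity system. No section says how a recorded waterbirth without an immersion analgesia entry is to be classed.

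Pool-use status has consequences beyond the label. Section 7 gives non-users a minimal data set and users a more extensive one. Sections 7, 9.3 and 9.4 send to the National Neonatal Research Database (NNRD) only babies whose mothers used a pool.

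On the comparison itself, section 5 states the aim as waterbirth against leaving a pool before birth, among low-risk women who used a pool in labour. Section 7 limits the comparator (Group 2) to low-risk women who left for non-clinical reasons. Neither section sets a time of leaving relative to birth. The background (section 4) puts the practical question more narrowly: "evidence continues to be lacking as to whether women should be encouraged to leave, or remain in, the pool for birth". Section 5.4 adds "Time of last leaving pool" to the maternity system as a new item, so it is available for prospective births.

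**The concern.** Two separate matters follow from one definition.

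The first is classification. An analgesia field and a place-of-birth field are different records. If only the analgesia field defines pool use, a woman whose baby is recorded as born in water, but whose analgesia entry names something else, falls on the non-user side. She would then get the minimal extract and no NNRD match, and could not contribute properly to Group 1. A rule about what is extracted and linked is hard to repair at analysis.

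The second is the make-up of Group 2. A woman who had a bath early in labour, got out by choice and gave birth many hours later stands in the comparator alongside a woman who got out during the second stage. Only the second woman clearly faced the choice of staying in for the birth. If early leavers tend to have higher event rates, for example through longer labours, the comparator rate rises. In a non-inferiority comparison that makes the conclusion easier to reach for both primary outcomes.

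**Working it through.** **Classification under the text of 9.6.4**

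| Record | Analgesia rule | Opening sentence of 9.6.4 | Result |
|---|---|---|---|
| Immersion analgesia entered, left early in labour by choice | pool user | included | Group 2 |
| Immersion analgesia entered, left in second stage by choice | pool user | included | Group 2 |
| Born in water, no immersion analgesia entry | not a pool user | included (she used water immersion) | conflict, unresolved |

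The third row is the gap in wording. The accrual figures in 9.6.1 (6,600 waterbirths in 2015; 6,037 at 18 sites in 2016) count recorded waterbirths, not waterbirths that also carry an analgesia entry.

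**The plan's own sample sizes**

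Inputs from 9.6.1: event rates p of 4.6% (nulliparous OASIS), 1.6% (parous OASIS) and 5% (neonatal composite); margins m of 1.0, 0.6 and 1.0 points; one-sided 5%; 90% power; true difference zero.

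n per group = (1.645 + 1.282)² × 2p(1 − p) / m², where (1.645 + 1.282)² ≈ 8.564.

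- Nulliparous: 8.564 × 2 × 0.046 × 0.954 / 0.01² ≈ 7,517 (stated 7,500)
- Parous: 8.564 × 2 × 0.016 × 0.984 / 0.006² ≈ 7,491 (stated 7,500)
- Neonatal: 8.564 × 2 × 0.05 × 0.95 / 0.01² ≈ 8,136 (stated 8,100)

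The stated sizes reproduce. The point does not depend on an error in them.

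**If waterbirths were lost (assumed 2–20%, not replaced)**

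Power = Φ( m / √[p(1 − p)(1/n_water + 1/n_land)] − 1.645 ).

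At 20% loss for nulliparous OASIS, n_water = 6,000 and n_land = 7,500. The standard error is √(0.043884 × 0.0003) = 0.00363, and power = Φ(2.756 − 1.645) = 86.7%. From about 90%, power falls to 89.7–86.7% (nulliparous), 89.8–86.8% (parous) and 89.6–86.6% (neonatal). The loss of power is small. Whether the lost births differ from the others cannot be judged from the protocol.

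**If early leavers are in Group 2**

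The protocol gives neither the share f of Group 2 that left early nor their risk ratio RR against later leavers. Both are assumptions here.

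Shift in comparator rate = p × f × (RR − 1), before any adjustment.

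| Outcome | p | Margin | f 20–50%, RR 1.25–1.5 | f 10–50%, RR 1.2–2.0 |
|---|---|---|---|---|
| Neonatal composite | 5.0% | 1.0 | 0.25–1.25 points | 0.10–2.50 points |
| Nulliparous OASIS | 4.6% | 1.0 | 0.23–1.15 points | 0.09–2.30 points |
| Parous OASIS | 1.6% | 0.6 | 0.08–0.40 points | 0.03–0.80 points |

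If RR were below 1 the sign would reverse. With f = 25% and RR = 0.8, the neonatal shift is 5.0 × 0.25 × (−0.2) = −0.25 points, which would work against non-inferiority.

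**What a shift would do to the neonatal conclusion**

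Take 8,100 per group, water at 6% and later leavers at 5%, so true harm sits at the margin. The observed land rate is 5% plus the shift. Non-inferiority is concluded if the observed difference is below 0.01 − 1.645 × SE.

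- Shift 0: 5%, by construction
- Shift 0.25: SE = √[(0.06 × 0.94 + 0.0525 × 0.9475)/8,100] = 0.00362; limit 0.00405; Φ((0.00405 − 0.0075)/0.00362) = 17%
- Shift 0.50: SE = 0.00366; limit 0.00398; Φ((0.00398 − 0.0050)/0.00366) = 39%

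**What the stated analyses cover**

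Table 1 in 9.6.5 marks duration of labour as a candidate covariate for OASIS but not for the neonatal composite. The sensitivity analyses planned for both primary outcomes are a propensity score analysis and an instrumental variable analysis. Neither is said to use the time of leaving.

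**The case against.** A reader might infer that the study compares the wrong groups. The protocol does not support that. The aim in section 5 and Group 2 in section 7 have no timing limit, and section 3 expressly includes conventional baths, so a voluntary early leaver is inside the declared comparison. The mismatch is only with the narrower decision described in the background. Nor is immersion counted at just any time: the rule applies to labour, and section 4 says "Women enter the warm water in established labour".

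A reader might also infer that waterbirths without an analgesia entry are certain to be lost. That goes too far. The opening sentence of 9.6.4 would take them in, waterbirth is defined and recorded in its own right, and section 9.6.2 refers spurious data to the SAP. What stands is that two sentences of one section point different ways, and that extraction and linkage depend on the answer.

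A third tempting reading is that the design will make waterbirth look safer. Direction and size rest wholly on assumed inputs. The arithmetic above is unadjusted, whereas the main model is adjusted and may include duration of labour for OASIS. Excluding exits for clinical need also removes some higher-risk leavers where the reason is known. The reason for leaving is, however, a new item, and the retrospective births used for OASIS are not said to carry it.

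Finally, the SAP is not at hand and may use the leaving time. The point is confined to what the protocol states.

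**Conclusion.** The point holds in limited form. The pool-use rule in 9.6.4 is ambiguous for a recorded waterbirth without an immersion analgesia entry. This matters because pool-use status controls the extract and the NNRD linkage. On power alone the effect is minor: a fall from about 90% to about 87% even at an assumed 20% loss.

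The rule also places early voluntary leavers in Group 2. That is consistent with the stated aim but broader than the leave-or-remain question. No analysis stated in the protocol uses the leaving time, and duration of labour is a candidate covariate for one primary outcome only. If early leavers carry 1.25–1.5 times the risk and make up 20–50% of Group 2, the unadjusted shift is 0.25–1.25 points for the neonatal composite, against a margin of 1.0. A shift of 0.25 or 0.50 points would raise false non-inferiority at the margin from 5% to about 17% or 39%. These figures show only that the question is worth answering. The actual size and direction cannot be derived from the protocol. The changes should be made, but the primary comparison does not need to be redefined.

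**What to change.** - In 9.6.4, define pool use as water immersion analgesia recorded OR birth recorded in water. Apply the same definition to the extraction and NNRD linkage rules in sections 7, 9.3 and 9.4.
- For both primary outcomes, pre-specify a supportive analysis in prospective births, limited to women still in the water at the start of the second stage. This depends on the maternity system recording that time: it is not among the new items in section 5.4, so confirm availability first.
- Report the distribution of time from last leaving the pool to birth in Group 2.
- Do not use a fixed interval before birth as the main restriction. It selects on how long labour lasted after exit, dropping women with a long remaining labour and keeping those with quick births. At most, show such intervals as descriptive strata.

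The primary comparison stays as worded. The cost is one sentence carried through the data rules, one added analysis and one table. The supportive analysis will have fewer comparator women, will cover prospective births only and will give wider intervals. If the start of the second stage is not recorded, only the descriptive part can be done.

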### 7 Study design and setting

A natural experiment using a cohort design with a qualitative component will answer the study objectives by using a combination of data captured retrospectively and prospectively in electronic NHS maternity and neonatal information systems. The qualitative component will explore factors associated with high and low rates of pool use; data will be gathered in online discussion groups, focus groups and one-to-one interviews with key stakeholders, including mothers/to be.

To answer all research objectives approximately 600,000 individual computerised maternity records held on secure NHS servers at around 30 NHS sites, covering the period January 2015 – November 2020 will be accessed. To provide necessary denominator data, and to be able to compare characteristics of pool users and non-pool users, a minimal data set will be extracted relating to women who did not use a pool in labour, whilst a more extensive dataset will be extracted for women who did use a pool in labour. An important clinical question is whether there is a differential effect of waterbirth on severe perineal trauma (OASIS) amongst nulliparous and parous women. To undertake this subgroup analysis will require a necessarily large sample (30,000). As data relating to perineal trauma and waterbirth are already captured, and to avoid unnecessarily prolongation of the study, this analysis will use a combination of retrospective and prospectively collected data, including births from 2015 to 2020.

The sample required for the neonatal primary outcome is smaller (16,200) and, as all essential data are not currently collected for one component of this composite outcome (antibiotic administration within 48 hours of birth on postnatal wards) additional data fields will to be added to maternity systems at participating NHS sites. Therefore, we will collect these data on births prospectively during the period June 2018 to November 2020.

Some neonatal outcomes of interest, including neonatal hypoxia, respiratory support or neonatal mortality, are already held by study sites or by the National Neonatal Research Database (NNRD). Where available and where the risk status, and pool usage of mothers can be determined, retrospective data will be utilised to increase the power of the analysis around secondary neonatal outcomes.

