### 9.3 Study Procedures

To answer the research questions, demographic and clinical data relating to all births at participating sites during the period of retrospective and prospective data collection will be extracted as follows:

- 1. Maternity sites will be recruited by Cardiff University and all required permissions obtained.
- 2. Data relating to births from January 2015 onwards and captured in EuroKing® prior to site opening will be extracted and transferred to Cardiff University. This retrospective data will be identified by EuroKing® mother and baby numbers only and contribute to the maternal outcomes for the study.

- Additional data items essential to the study, but not currently in the E3 system, including a screening question to identify women with complicating factors on pool entry, will be added to the system at each participating site.
- 4. Following three months of prospective data collection, and each quarter thereafter, data relevant to the study and captured in E3 systems at each study site will be extracted by EuroKing®.
- 5. EuroKing® will allocate each mother and baby a linking identifying number, remove NHS and hospital numbers, and other identifiable variables and forward the data to Cardiff University.
- 6. On a quarterly basis, the NHS and EuroKing® numbers of all babies born at units during that period, and whose mother used a pool in labour, will be extracted and passed onto the NNRD for matching. The transfer process will be managed by EuroKing® throughout the duration of the study. E3 systems are installed locally on premises at each NHS Trust / Health Board therefore each set of data extractions must be managed on a site by site basis by EuroKing®.

To Note. Data extraction from sites on a quarterly basis is required as less frequent extractions may result in challenges for sites with less powerful servers, and ensures timely matching of maternal and neonatal data between EuroKing® and the NNRD.

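### Waterbirth is defined to include births begun in water and completed on land, but the item that identifies them exists only from site opening, while maternal outcomes pool births from January 2015

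*Protocol*

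**What the plan says.** Section 9.6.4 defines waterbirth as "A birth in which the fetus is partially or totally expelled under water". It gives the purpose as follows: "To capture births commenced in, but completed, out of water, such as in the event of shoulder dystocia", or a previously unrecognised breech. Such births are thus meant to stay in the waterbirth group.

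Section 5.4 says of new data items: "Additional data items with accompanying background development required to fully answer the research aims will be added to E3 systems at study sites". The list includes "Partial birth in water (breech / shoulder dystocia"), and also the reason for leaving the pool and the time of last leaving it. On timing, the same section says of outcomes not yet captured that at site opening the "systems at sites will be amended to prospectively collect these data".

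Section 7 justifies using older records for OASIS: "As data relating to perineal trauma and waterbirth are already captured". It then says "this analysis will use a combination of retrospective and prospectively collected data, including births from 2015 to 2020". Section 9.3 says that the retrospective records are identified by "mother and baby numbers only and contribute to the maternal outcomes for the study".

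The neonatal primary outcome uses prospective births only (section 7, June 2018 to November 2020).

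**The concern.** One exposure has two operational definitions. From site opening, a birth begun in water and completed on land can be recognised and put in the waterbirth group. Before that, no item marks it. If the older field recorded the place where the birth was completed, such a birth appears as a land birth in a pool user and enters the comparator.

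These births are not a random subset. They are the ones in which a complication arose while the woman was in the water. Moving them to the comparator would lower the event rate in the waterbirth group and raise it in the other. In a non-inferiority safety study that pushes towards reassurance.

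The outcomes at stake are OASIS (maternal primary), shoulder dystocia and its management (maternal secondary, and singled out in section 4 as an emergency that the pool might complicate), and brachial plexus injury (infant secondary, where section 5.4 allows retrospective data). Section 9.6.5 says that secondary outcomes will have non-inferiority testing.

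**Working it through.** **Can anything else in the protocol catch these births?**
- Section 7 restricts the comparator to women who left the pool for non-clinical reasons. That could screen them out, but the reason for leaving is itself a new item and is absent from retrospective records.
- The sensitivity analyses named after section 9.6.6 (propensity score, instrumental variable) address selection, not misrecorded exposure.
- Section 9.6.2 leaves missing and spurious data to the SAP. A birth coded by place of completion is not missing; it looks like a valid land birth.

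**The plan's own figure.** With n = 2p(1 − p)(1.645 + 1.282)²/m², 90% power and one-sided 5%:
- nulliparous, p = 4.6%, m = 1.0 point: 7,517 per group;
- parous, p = 1.6%, m = 0.6 point: 7,491 per group.

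Both match the stated 7,500. The sample size is not in dispute and supplies the base for what follows.

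**Retrospective share.** January 2015 to May 2018 is 41 of the 71 months to November 2020: 41/71 = 0.577. This is calendar time, not births. Staggered opening raises it; the growth in waterbirths mentioned in section 9.6.1 lowers it.

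**Shoulder dystocia (illustration).** Assume a true rate of 1% in both groups of 15,000, so 150 cases each. Let q be the share of pool cases both completed on land and coded as land in the retrospective period. Neither figure is in the protocol.

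Moved = 150 × q × 0.577. Rates are (150 − moved)/(15,000 − moved) and (150 + moved)/(15,000 + moved).

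| q | Moved | Water | Land | Ratio |
|---|---|---|---|---|
| 0 | 0 | 1.00% | 1.00% | 1.00 |
| 0.25 | 21.7 | 0.86% | 1.14% | 0.75 |
| 0.50 | 43.3 | 0.71% | 1.29% | 0.56 |
| 0.75 | 65.0 | 0.57% | 1.43% | 0.40 |

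**Nulliparous OASIS (illustration).** Take 7,500 per group, a 4.6% base rate (345 cases) and no true difference. Let f be the partial share of waterbirths and k the OASIS risk ratio in them, and suppose that all retrospective partial births are coded as land.
- f = 0.25%, k = 2: moved 7,500 × 0.0025 × 0.577 = 10.8 births, carrying 10.8 × 0.092 = 1.0 case. Water 344.0/7,489.2 = 4.593%, land 346.0/7,510.8 = 4.607%. Shift 0.01 point.
- f = 1%, k = 4: moved 43.3 births, carrying 43.3 × 0.184 = 8.0 cases. Water 337.0/7,456.7 = 4.52%, land 353.0/7,543.3 = 4.68%. Shift 0.16 point.

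**Effect on the test.** With a true nulliparous difference exactly at the 1.0-point margin, f = 1% and k = 3, the expected observed difference is 0.90 point, with a standard error of about 0.36 point. The chance of wrongly concluding non-inferiority is Φ((1.00 − 0.90)/0.36 − 1.645), or about 9% instead of 5%. At f = 2% and k = 5 the difference falls to about 0.58 point and the error reaches about 31%, but both inputs are at the far end of what was assumed. For parous women the f = 1%, k = 3 case gives 0.57 point against 0.6, and about 7%.

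**The case against.** A reader might infer that the retrospective data definitely place these births in the comparator and that the bias is therefore established. The documents do not support that. No section describes how the earlier field was completed. A midwife may have recorded a partly submerged birth as a waterbirth, in which case the new item only separates partial from complete waterbirths and nothing has moved. The absence of a separate flag does not show that these births were filed as land. This objection stands, and it is why the direction is conditional.

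The illustrative sizes are also assumption-driven. The 1% dystocia rate, the land-coded share q and the raised OASIS risk are not in the protocol, and q = 0 is a live possibility. The OASIS upper end of 0.16 point also sits loosely with the other illustration: 1% dystocia with at most 75% moved gives f = 0.75%, and about 0.12 point at fourfold risk, unless breech supplies the rest. Further, section 4 is worried about delay in managing dystocia rather than its incidence, and only the shift in incidence is calculated here; no effect on management or brachial plexus injury has been quantified. Retrospective use for infant outcomes is conditional on risk status and pool use being known, and is worded as description. These points limit the size of the claim.

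It can also be said that extra sensitivity analyses belong in the SAP. That is fair as to where they are specified. It does not remove the inconsistency, because the protocol itself fixes the exposure definition and treats waterbirth as available in the older records.

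**Conclusion.** The point holds as an inconsistency in the exposure definition. The section 9.6.4 definition cannot be verified or applied uniformly to births before site opening, and nothing else in the protocol compensates.

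Whether this biases the results depends on earlier recording practice, which the protocol does not give. If partial births were coded as waterbirths, the bias is zero. If any were coded by place of completion, it favours water. For OASIS it is then probably small, 0.01 to 0.16 point against a 1.0-point nulliparous margin under the assumptions shown; it becomes material only if partial births are about 1% or more of waterbirths and carry clearly raised risk. For shoulder dystocia it could be large, and brachial plexus injury is exposed in the same way where retrospective data are used.

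Two further inferences should be resisted: that the pooled OASIS analysis is invalid, which these figures do not show, and that the neonatal primary outcome is affected, which it is not, being prospective only.

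**What to change.** In sections 9.6.4 and 9.6.5:

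1. State that the partial-birth part of the waterbirth definition can be applied only from site opening, and state how the maternity system recorded such births before the new item, if this can be established.
2. Keep the pooled OASIS analysis, and add (a) an analysis of prospective births only and (b) a worst-case analysis that moves retrospective pool users with shoulder dystocia or breech coded as land births into the waterbirth group.
3. For shoulder dystocia, its management and brachial plexus injury, base the water-versus-land comparison on prospective births, with pooled data as supportive, unless the earlier field is shown to have coded partial births as waterbirths.

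The cost is some wording and extra runs on data the study will already hold. The real downside is precision: by calendar time about 58% of the period drops out of the main comparison for those rare secondary outcomes, which is why item 3 should lapse if the earlier coding proves sound.
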